#### **8.2.9.1. Criteria for Dose Reduction**

Dose reductions are not allowed during the DLT evaluation period, except for subjects who experience DLTs. Subjects who experience toxicities during the DLT evaluation period that do not meet the protocol specified definition for DLTs (Section 8.2.6) may either continue at their assigned dose or withdraw from the study at the discretion of the investigator and/or the subject. If a subject withdraws for any reason other than DLTs prior to the completion of the DLT evaluation period, that subject will be considered non-evaluable and will be replaced.

Once the dosage has been reduced for toxicity for a subject, future escalation will not be permitted.

Any of the AEs listed in [Table 10](#) after the DLT evaluation period will require a dose interruption and/or reduction.

Dose reductions may be considered for AEs occurring after the DLT evaluation period that do not meet the criteria listed in [Table 10](#) after discussion between the investigator and the sponsor.

Guidance for dose reduction is as follows:

- Subjects requiring dose reductions for toxicities occurring on or BEFORE Cycle 1 Day 28 (such as subjects who have experienced DLTs and recovered) should be reduced to the next lowest dose level that has been shown to be tolerated by at least 3/3 or 5/6 subjects.
- Subjects requiring dose reduction for toxicities occurring AFTER Cycle 1 Day 28 may be reduced to the next lowest dose level that has been shown to be tolerated by at least 3/3 or 5/6 subjects.

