#### **8.2.9.3. Treatment Delay**

Treatment may be delayed up to 4 weeks until treatment-related toxicities (excluding alopecia) resolve to either  $\leq$  Grade 1 or baseline levels. Treatment may restart either at the same, or a reduced dose level, at the investigator's discretion or as described in Section [8.2.9.1](#).

During the DLT evaluation period, a treatment interruption that causes a subject to miss 3 doses (need not be consecutive) for reasons other than DLTs will make a subject non-evaluable for DLTs and will necessitate the replacement of that subject in the dosing cohort.

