#### **8.2.9.4.2. Dose Modification and Management of Pneumonitis**

Pneumonitis has been reported with CC-122. The diagnosis should be considered in subjects presenting with nonspecific respiratory signs and symptoms such as hypoxia, pleural effusion, cough, dyspnea, or interstitial pulmonary infiltrates, and in whom infectious, neoplastic and other causes are excluded by appropriate investigations. Subjects should be specifically advised to promptly report any new or worsening respiratory symptoms they experience.

CC-122 dosing for those with radiological features suggestive of noninfectious pneumonitis but with minimal (Grade 1) symptoms may be interrupted per the investigator's discretion. For drug-related Grade 2 pneumonitis, CC-122 treatment should be interrupted and corticosteroids may be indicated. Once symptoms have resolved completely, CC-122 may be reintroduced at the next lower dose level. For drug-related Grade 3 or 4 pneumonitis, CC-122 must be permanently discontinued and corticosteroids used until clinical symptoms have resolved.

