#### **8.2.9.4.3. Dose Modification and Management of Tumor Flare Reaction**

Subjects in this study should be monitored for tumor flare. Tumor flare reaction (TFR) is defined as a sudden and tender increase in the size of the disease bearing sites, including the lymph nodes, spleen and/or the liver often accompanied by low-grade fever, nonpruritic diffuse rash and in some cases increase in the peripheral blood lymphocyte counts. Tumor flare usually occurs within the first cycle of treatment. Tumor flare reaction may mimic progression of disease (PD); however, the TFR will generally subside over time. Therefore, careful monitoring and evaluation is important prior to discontinuing a study subject for PD in the initial cycles of CC-122 therapy.

There are currently no laboratory or radiological tests that distinguish TFR from PD. The distinction should be made on clinical grounds, incorporating observations such as associated physical findings, laboratory findings, and pace of disease before and after institution of treatment. Tumor flare will be recorded as an AE (graded using the NCI CTCAE 3.0 criteria) and not as PD.

Treatment of the TFR is up to the discretion of the investigator, depending on the severity and clinical situation. Recommendations for treatment are outlined in [Table 10](#). Refer to [Table 10](#) for further instructions and dose modifications for Grades 3 and 4 TFR. In mild to moderate cases, it is suggested that CC-122 be continued along with symptomatic treatment as outlined above. In more severe cases, CC-122 should be interrupted, as indicated in [Table 10](#).

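### For Cycle 1 toxicity short of a DLT, Section 8.2.9.1 does not name interruption while later sections allow or require it, so the same event can be counted in three ways

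*Combined protocol and SAP*

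**What the plan says.** Protocol Section 8.2.9.1 opens with the rule "Dose reductions are not allowed during the DLT evaluation period, except for subjects who experience DLTs". For toxicities in that period that are not DLTs, it says that subjects "may either continue at their assigned dose or withdraw from the study at the discretion of the investigator and/or the subject". Anyone who withdraws before the period ends for a reason other than a DLT is non-evaluable and replaced. On Table 10, the same section says that the listed events "after the DLT evaluation period will require a dose interruption and/or reduction".

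Other sections treat interruption differently:

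- Section 8.2.9.3: "Treatment may be delayed up to 4 weeks until treatment-related toxicities (excluding alopecia) resolve to either" Grade 1 or lower or baseline, with no cycle limit. It then has a Cycle 1 rule: "During the DLT evaluation period, a treatment interruption that causes a subject to miss 3 doses (need not be consecutive) for reasons other than DLTs" makes the subject non-evaluable.
- Section 8.2.9.4.1 says dosing should be held when troponin-T is above normal together with a defined BNP rise or cardiac findings. No cycle is named.
- Section 8.2.9.4.2: "For drug-related Grade 2 pneumonitis, CC-122 treatment should be interrupted". No cycle is named.
- Section 8.2.9.4.3: "Tumor flare usually occurs within the first cycle of treatment"; management is referred to Table 10.
- The Table 10 row for Grade 4 neutropenia calls for a hold until Grade 1 or lower, then a restart at a lower dose level. The table itself states no cycle limit.

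Table 8 makes Grade 4 neutropenia a DLT if it lasts more than 7 days. Separately, it makes any related event that requires a dose reduction during the DLT period a DLT.

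**The concern.** A site facing a Cycle 1 toxicity that is not yet a DLT finds two options in 8.2.9.1, neither of them a hold, and finds holds permitted or required elsewhere. It also cannot tell whether Table 10 applies in Cycle 1. Section 8.2.9.1 points to later cycles, whereas 8.2.9.4.3 sends the investigator to Table 10 for an event that it places mainly in the first cycle.

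This bears on safety, because the passages differ on whether dosing goes on. It also bears on the primary endpoint. DLT status depends partly on duration and partly on whether a reduction was needed, and evaluability depends on doses taken. The passage that a site follows can therefore decide whether a subject enters the DLT numerator, enters only the denominator, or leaves the cohort and is replaced.

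**Working it through.** **1. The plan's own figure.** Four weeks at 5 doses gives 20 planned doses in Cycle 1. Section 8.2.4 requires 85%: 0.85 × 20 = 17, as stated. A subject without a DLT may therefore miss 3 doses under 8.2.4. Under 8.2.9.3, missing 3 already makes the subject non-evaluable.

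**2. Doses lost to a hold.** I counted missed doses for every placement of one unbroken hold lying wholly within the 28 days (5 on, 2 off).

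| Hold (calendar days) | Doses missed, min to max | Evaluable without a DLT? |
|---|---|---|
| 4 | 2 to 4 | Both sections, at best (2 missed) |
| 5 | 3 to 5 | 8.2.4 only, at best (3 missed) |
| 6 | 4 to 5 | Neither |
| 7 | 5 | Neither (15/20 = 75%) |

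**3. One event, three classifications.** Take a Cycle 1 Grade 4 neutropenia.

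- *DLT.* It lasts more than 7 days. Alternatively, the site applies the Table 10 row, and the restart at a lower dose can meet the Table 8 dose-reduction row whatever the duration. The logic is circular: 8.2.9 bars a Cycle 1 reduction unless there is a DLT, while Table 8 makes the need for a reduction a DLT.
- *Evaluable, no DLT.* It resolves within 7 days with dosing continued or after a short hold.
- *Non-evaluable and replaced.* The subject withdraws (8.2.9.1), or is held long enough to fail step 2 without meeting a DLT criterion.

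**4. Holds required for events that need not be DLTs.** Grade 2 pneumonitis is below the Grade 3 threshold in the non-hematologic row of Table 8. A troponin-T and BNP rise without symptoms can fall under the note to Table 8 that leaves out isolated laboratory changes. For both, a later section asks for a hold that 8.2.9.1 does not list.

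**5. Effect on the decision (Section 8.2.7).** One more subject with a DLT turns 0/3 (escalate) into 1/3 (expand), or 1/6 (tolerated) into 2/6 (non-tolerated).

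**6. Illustration with assumed rates.** The documents give no Cycle 1 rate of Grade 4 neutropenia and no recovery time, so these inputs are mine. With DLT probability p per evaluable subject, P(escalate) = (1−p)³ + 3p(1−p)⁵. Central assumptions: other DLTs q = 10%, Grade 4 neutropenia g = 20%, share lasting more than 7 days if dosing continues s = 50%. Ranges: q 5–15%, g 10–30%, s 25–100%.

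| Handling | p | P(escalate) | Range over the grid |
|---|---|---|---|
| All continue | 0.10 + 0.90×0.20×0.50 = 0.190 | 0.73 | 0.30–0.95 |
| Short hold always prevents more than 7 days | 0.100 | 0.91 | 0.81–0.97 |
| Held subjects replaced | 0.10/(1 − 0.90×0.20) = 0.122 | 0.87 | 0.71–0.97 |
| Table 10 restart makes each case a DLT | 0.10 + 0.90×0.20 = 0.280 | 0.54 | 0.30–0.82 |

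The table shows the possible size of the effect. It is not an estimate for this trial.

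**The case against.** The strongest reply is that 8.2.9.1 concerns dose reduction. Its two-option sentence follows the ban on reductions, so staying on the assigned dose may simply mean without a reduction. Interruption has its own section, 8.2.9.3; Section 8.2.4 tolerates missed doses, and Section 6.4 plans for an interruption before the Day 10–12 PK sampling. Read together, a Cycle 1 hold is possible and a reduction is not. This reading is reasonable, and it means the text does not force a site to choose between dosing on and withdrawal. It does not settle the matter, because the Table 10 sentence in the same section covers interruption as well as reduction and places both after the DLT period.

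The tumor flare example is weaker than it looks. Table 10 continues dosing for Grade 1–2 flare, which agrees with 8.2.9.1, and related, clinically relevant Grade 3–4 flare would generally be a DLT. It shows only that Table 10 is meant to be consulted in Cycle 1.

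Safeguards exist. Cycle 1 is inpatient as a rule, about 3 sites take part, and the investigators sit on the SRC. Event dates, action taken and dosing data are already collected. These limit divergence and make it traceable, but they do not say which rule applies. The summary for amendment 03 reports safety confirmed at 2, 3 and 4 mg AIC, so what remains exposed is chiefly the formulated-capsule cohort of at least 6 subjects and the exploratory comparison of DLT rates between formulations.

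**Conclusion.** The passages conflict on interruption in Cycle 1 and on the scope of Table 10, and the conflict can change the primary DLT count. In cohorts of 3 to 6, one subject is enough to change the decision. How often this would happen cannot be derived from the documents.

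Three stronger conclusions are tempting, and the documents do not support them:

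- *That Grade 4 neutropenia must be held in Cycle 1.* Section 8.2.9.3 permits a delay. The only required neutropenia hold is in Table 10, whose mandatory use 8.2.9.1 ties to later cycles.
- *That a hold brings Grade 4 neutropenia to 7 days or less.* No recovery time is given.
- *That the size can be read from the 30.6% Grade 3–4 neutropenia at 4 mg 5/7 in the DLBCL-2 cohort (Section 1.1.3).* At that rate, 1 − 0.694³ = 67% of 3-subject cohorts and 1 − 0.694⁶ = 89% of 6-subject cohorts would contain a case. Those figures cover both grades, without the Cycle 1 or 7-day restriction, in another study. They do not measure reclassified DLTs and should not be used here.

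The conclusion rests on the wording and on the dose count, not on the assumed rates in the illustration.

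**What to change.** Reconcile Section 8.2.9.1 with 8.2.9.3, 8.2.9.4.1 to 8.2.9.4.3, Table 10 and the dose-reduction row of Table 8. In one place, state:

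- whether interruption is an option for non-DLT toxicity in Cycle 1;
- which Table 10 rows apply in Cycle 1;
- how such events count for DLT and for evaluability, including a restart at a lower dose and a subject who misses exactly 3 doses (8.2.4 against 8.2.9.3).

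Amend the Table 10 scope sentence in 8.2.9.1 to match. The clinical rule is the sponsor's choice. Optionally, show hold dates for each Cycle 1 Grade 4 neutropenia in the SRC listing.

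The cost is a short wording amendment and, if wanted, one listing column built from data already collected. No extra subjects or visits are needed.

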**Table 9: Example of Dose Reduction Steps**

Current Dose	2.0 mg intermittent 5/7 days	3.0 mg intermittent 5/7 days	4.0 mg intermittent 5/7 days
Dose reduction -1	1.0 mg intermittent 5/7 days	2.0 mg intermittent 5/7 days	3.0 mg intermittent 5/7 days
Dose reduction -2	Discontinue	1.0 mg intermittent 5/7 days	2.0 mg intermittent 5/7 days
Dose reduction -3	-	Discontinue	Discontinue

#### **8.2.9.2. Intra-subject Escalation**

Intra-subject dose escalation beyond the dose initially assigned to a subject is not permitted during the DLT evaluation period. Those continuing to take CC-122 longer term may, following approval by the SRC, have their dose level increased, provided that the alternative dose level has been shown to be well-tolerated in at least one cohort of other subjects in this study.

To be considered for intra-subject dose escalation, a subject must not have experienced  $\geq$  Grade 3 toxicities at their assigned dose level.

#### **8.2.9.3. Treatment Delay**

Treatment may be delayed up to 4 weeks until treatment-related toxicities (excluding alopecia) resolve to either  $\leq$  Grade 1 or baseline levels. Treatment may restart either at the same, or a reduced dose level, at the investigator's discretion or as described in Section [8.2.9.1](#).

During the DLT evaluation period, a treatment interruption that causes a subject to miss 3 doses (need not be consecutive) for reasons other than DLTs will make a subject non-evaluable for DLTs and will necessitate the replacement of that subject in the dosing cohort.

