**Table 8: DLT Criteria**

Toxicity	
Non-hematologic AEs	A clinically relevant non-hematologic AE that is suspected to be related to CC-122 and that commences during the DLT evaluation period and is $\geq$ Grade 3 EXCEPT for: 
 
Grade 3 rash of the acneiform or maculopapular type lasting <math>\leq</math> 4 days (with optimal medical management)
 
Grade 3 diarrhea or vomiting lasting less than 72 hours (with optimal medical management)
 

Laboratory abnormalities	A clinically relevant laboratory abnormality that is suspected to be related to CC-122 and that commences during the DLT evaluation period and is $\geq$ Grade 3
Hematologic	Any febrile neutropenia
	Grade 4 neutropenia lasting $>$ 7 days
	Grade 4 thrombocytopenia lasting $>$ 24 hours or thrombocytopenia of any grade requiring platelet transfusions
	Any Grade 3/4 thrombocytopenia with clinically significant bleeding
Hepatic	Grade 4 liver function tests (LFTs) or Grade 3 ALT with Grade 2 or higher bilirubin will be considered a DLT, irrespective of underlying attribution  However, other Grade 3 LFTs due to disease progression in the liver will not be considered DLTs
Other adverse events	Any adverse event suspected to be related to CC-122 and necessitating a dose reduction during the DLT evaluation period

Toxicities will be considered treatment-related unless clearly attributed to an alternative etiology (for example, tumor progression) by the investigator. Toxicities must be clearly not related to disease progression, medical procedures or intercurrent illnesses in order to be considered dose-limiting.

Isolated laboratory changes without associated clinical signs or symptoms will not be included in this definition. These findings will be discussed and reviewed by the SRC.

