### **8.2.9. Permitted Dosing Adjustments**

No dose reduction is allowed during the DLT evaluation period, except for subjects who experience DLTs. Subjects who experience DLTs during the DLT evaluation period will be allowed to resume CC-122 at a reduced dose once their toxicity recovers to Grade 1 or baseline, provided recovery occurs within 28 days of interrupting dosing. Dose reductions for non-dose-limiting toxicities are allowed after the DLT evaluation period after consultation with the sponsor.

Those continuing to take CC-122 beyond Cycle 1 may, following approval by the SRC, have their dose level increased, provided that the alternative dose level has been shown to be well-tolerated in at least one cohort of other subjects in this study. In these instances, additional PK evaluations at the higher dose level will be collected.

If a dose reduction is indicated, the next lower dose level will be selected. Two dose reductions are allowed, with the exception of the starting dose for which only one dose reduction is allowed. If any subject continues to experience unacceptable toxicity after 2 dose reductions, CC-122 will be discontinued permanently.

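### In Cycle 1 a related toxicity that leads to a dose reduction counts as a DLT, but the same toxicity leading to withdrawal is replaced and not counted; the restart text in 8.2.9.3 does not close the gap

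*Combined protocol and SAP*

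**What the plan says.** All references are to the protocol.

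- **Table 8 (8.2.6), last row**, lists as a DLT: "Any adverse event suspected to be related to CC-122 and necessitating a dose reduction during the DLT evaluation period". It sets no minimum grade.
- **8.2.9**: "No dose reduction is allowed during the DLT evaluation period, except for subjects who experience DLTs". Section 8.2.9.1 repeats this bar.
- **8.2.9.1**, on Cycle 1 toxicities that are not DLTs: such subjects "may either continue at their assigned dose or withdraw from the study at the discretion of the investigator and/or the subject". It continues: "If a subject withdraws for any reason other than DLTs prior to the completion of the DLT evaluation period", the subject is non-evaluable and is replaced. The same section makes Table 10 binding only later: a listed event "after the DLT evaluation period will require a dose interruption and/or reduction".
- **8.2.9.3, first paragraph**, on restart after a hold: "Treatment may restart either at the same, or a reduced dose level, at the investigator's discretion or as described in Section" 8.2.9.1. It names no period. The second paragraph covers the DLT period: missing 3 doses for reasons other than DLTs "will make a subject non-evaluable for DLTs and will necessitate the replacement of that subject in the dosing cohort".
- **8.2.9.4.2**, on related Grade 2 pneumonitis: dosing is interrupted, then "Once symptoms have resolved completely, CC-122 may be reintroduced at the next lower dose level". No other restart dose is named, and Cycle 1 is not excepted.
- **8.2.4**: a subject without a DLT is evaluable with at least 17 of 20 doses; a subject with a DLT is evaluable after one dose.

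**The concern.** Dose decisions rest on the number of subjects with DLTs (8.2.7). Some related Cycle 1 toxicities meet no grade or duration criterion in Table 8, for example Grade 2 pneumonitis or Grade 3 neutropenia without fever. For these, the last row is the only route to a DLT, and it mentions reduction only. If the drug is reduced by one level, the event counts against the dose. If it is stopped for the same event, the subject leaves the denominator and a new subject takes the place. Replacement that depends on drug toxicity lowers the observed DLT rate.

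One subject can matter: 0 of 3 (tolerable) becomes 1 of 3 (expand), and 1 of 6 (compatible with the MTD) becomes 2 of 6 (non-tolerated). The decisions still open concern Cohort 4 (3 mg formulated capsules, at least 6 subjects) and any lower formulated dose. In healthy adults this formulation gave 16.29% higher AUCinf and 35.58% higher Cmax than the AIC capsules (1.1.3). The exploratory comparison of DLT rates between formulations (3.3) also needs one counting rule across cohorts.

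**Working it through.** **Evaluability figure.** Cycle 1 has 4 × 5 = 20 planned doses, and 0.85 × 20 = 17. This reproduces the threshold in 8.2.4.

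**One event, several actions.** Take related Grade 2 pneumonitis in Cycle 1. It is below Grade 3, so only the last row of Table 8 can make it a DLT.

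| Action in Cycle 1 | Text applied | Result |
|---|---|---|
| Hold, restart one level lower | 8.2.9.4.2 or 8.2.9.3; Table 8 last row; 8.2.4(b) | DLT, counted |
| Withdrawn for the event | 8.2.9.1 | Non-evaluable, replaced |
| Hold of 1–2 doses (18–19 of 20), same dose | 8.2.9.3 or 8.2.9.1; 8.2.4(a) | Evaluable, no DLT |
| 7-day hold, 5 doses missed (15/20 = 75%), same dose | 8.2.4(a); 8.2.9.3 | Non-evaluable, replaced |

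With exactly 3 missed doses (17/20 = 85%), 8.2.4 keeps the subject evaluable while 8.2.9.3 replaces the subject. The first two rows carry the point: the milder action counts and the stronger one does not.

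**Direction of the bias.** Let p be the share of subjects with a DLT under the other rows, and q the further share with an event of this kind.

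- All reduced and counted: per-subject rate r = p + q.
- All stopped and replaced: r = p/(1 − q).
- Difference: (p + q) − p/(1 − q) = q(1 − p − q)/(1 − q), which is positive whenever p + q < 1.

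Replacement therefore always lowers the rate. A mixture of the two actions falls in between.

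**Illustrative size.** The documents give neither p nor q. I assume p = 10% and vary q.

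- P(dose called tolerable) = (1 − r)³ + 3r(1 − r)⁵
- P(2 or more DLTs in 6) = 1 − (1 − r)⁶ − 6r(1 − r)⁵

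| q | r, counted / replaced | Tolerable, counted / replaced | 2+ of 6, counted / replaced |
|---|---|---|---|
| 5% | 15.0% / 10.5% | 81.4% / 89.7% | 22.4% / 12.5% |
| 10% | 20.0% / 11.1% | 70.9% / 88.7% | 34.5% / 13.7% |
| 20% | 30.0% / 12.5% | 49.4% / 86.2% | 58.0% / 16.7% |

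Example for q = 10%, counted: 0.8³ + 3 × 0.2 × 0.8⁵ = 0.5120 + 0.1966 = 0.7086. At q = 10% with p = 5% the tolerable figures are 81.4% / 96.8%; with p = 20% they are 49.4% / 66.0%.

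**The restart text.** 8.2.9 and 8.2.9.1 bar a Cycle 1 reduction unless the subject has a DLT. Table 8 makes a necessary reduction a DLT. Together these give one coherent rule: every Cycle 1 reduction for a related event is a DLT. But 8.2.9.3 offers the reduced restart at discretion, joined to 8.2.9.1 by an *or*, and 8.2.9.4.2 prescribes the lower dose without mentioning DLT status. Nor is there a Cycle 1 test for when a reduction is necessary, since 8.2.9.1 makes Table 10 mandatory only afterwards.

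**The case against.** - **The sections can be reconciled.** A reader might infer that four sections give four restart rules, or that the last row of Table 8 is circular. The documents do not support either. 8.2.9 and 8.2.9.1 state the same bar, and a necessary reduction is itself a DLT, so it falls within the exception. The first paragraph of 8.2.9.3 reads as a general rule to which the specific Cycle 1 bar applies. This stands; what remains is that the link is left unstated.
- **Stopping could be read as covered, being more than a reduction.** This is reasonable clinically, but 8.2.9.1 expressly allows withdrawal for a non-DLT toxicity and replaces the subject, and 11.2.5 lists discontinuation, interruption and reduction as separate actions.
- **The Safety Review Committee (SRC) sees these cases.** Table 8 mentions the SRC only for isolated laboratory changes, and a reader might infer that its review ends there. It does not: 4.1.1 and 8.2.1 put the cohort's safety data before it. This is a real safeguard, but the written rule still replaces the subject, and the SRC is given no criterion for counting the event.
- **The figures rest on assumptions, and few events may qualify.** Both are fair. Grade 2 pneumonitis must resolve completely before restart, so reduced restarts within Cycle 1 may be rare. Replacement also depends on missed doses or withdrawal, not on restart dose alone.
- **AIC escalation is done.** The Amendment 03 justification records safety confirmed at 2, 3 and 4 mg AIC, and 8.2.8 stops escalation at the global MTD. A reader might infer that those clearances are unsound; the documents report no Cycle 1 toxicity withdrawals that would show this.

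**Conclusion.** The point holds in a narrow form. As written, a related Cycle 1 toxicity that meets no other DLT row is counted if the dose is reduced and replaced if the subject is withdrawn for it, so the DLT rate is biased downward. That follows from the text and the algebra alone. The discretionary restart in 8.2.9.3 and the pneumonitis rule in 8.2.9.4.2 are a lesser defect: they fit the rest only under a reading that the protocol should state.

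The size is unknown. With p assumed at 10% and q from 5% to 20%, the gap in the chance of calling a dose tolerable runs from about 8 points (89.7 − 81.4) to 37 points (86.2 − 49.4). It compares all events reduced with all events stopped and is no estimate for this trial. The practical reach is Cohort 4, any lower formulated dose and the exploratory formulation comparison. Dosing after Cycle 1 is unaffected. A change worth considering, not a fault that undermines the study.

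**What to change.** 1. **Table 8, last row, and 8.2.9.1.** Extend the row to related events that require permanent discontinuation of CC-122 in the DLT period, alongside those that require a reduction. State in 8.2.9.1 that these subjects are evaluable under 8.2.4(b) and are not replaced. Withdrawal for other reasons is still replaced.
2. **8.2.9.3.** State that in the DLT period a reduced restart is allowed only if the event is recorded as a DLT; otherwise the subject restarts at the assigned dose. The SRC confirms the classification at the cohort review.
3. **8.2.9.4.2.** Keep the next-lower-dose restart for Grade 2 pneumonitis, which protects the subject. Add that in Cycle 1 this reduction, or stopping for the event, is a DLT.

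Cost: a few sentences and no new data, since action taken with the drug (11.2.5) and reason for discontinuation (section 12) are already recorded. The DLT definition becomes slightly wider. Cycle 1 discontinuations for related toxicity in the AIC cohorts should be re-read under the same rule for the exploratory comparison only, without reopening earlier SRC decisions. Whether a reduction or stop was needed remains a clinical judgement, and the missed-dose replacement rule is unchanged.
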